The final two years of the project are devoted to a randomized controlled trial (RCT) comparing the new CHTC+SUM to the standard CHTC protocol and testing the added efficacy of the CT component. A total of 70 couples were randomized to one of four conditions (standard

CHTC, CHTC +SUM, CHTC +CT, or CHTC +SUM and CT) in a factorial design. Follow-ups were completed online at 1-, 3-, and 6-months post-intervention.

Objectives

The purpose of the current pilot study was to test the feasibility, acceptability, and preliminary efficacy of two adjunct Couples HIV Testing and Counseling (CHTC) components: assertive communication training (CT) videos and a substance use module (SUM) module intended to facilitate a discussion around drug use and the formation of joint substance use goals. It was hypothesized that these two experimental components would significantly decrease the occurrence and severity of drug use. It was further hypothesized that these components would significantly reduce the occurrence of CAS with casual partners, a behavior which might increase HIV infection risk for the couple. Two variables relevant to intervention safety were also examined: the emergence of Intimate Partner Violence (IPV) and relationship dissolution post-intervention.

Trial Design

This study utilizes a factorial (2 X 2) randomized controlled trial (RCT) design to evaluate the efficacy of the We Test intervention components. Baseline assessment is conducted prior to randomization and the receipt of intervention (CHTC as usual, CHTC + SUM, CHTC + CT or CHTC+SUM+CT). Follow-up assessments are conducted at 1-, 3-, and 6-months post-baseline.

METHODS: Participants, Interventions and outcomes

Study setting

All study assessments and intervention sessions are conducted at the PRIDE Health Research Consortium affiliated with Hunter College of the City University of New York. PRIDE

is located centrally in Manhattan with easy access to a mass public transportation hub, linking it to the larger metropolitan area. Assessment and intervention sessions are conducted in private rooms.

Eligibility Criteria

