	STUDY PERIOD				
	Enrolment	Allocation	Post-allocation	Close-out	
TIMEPOINT	$-t_1$	0	1	3	6
ENROLMENT:					
Eligibility screen	X				
Informed consent	X				
Baseline	X				
Allocation		X			
INTERVENTIONS:					
CHTC					
CHTC + SUM					
CHTC + CT					
CHTC + SUM + CT					
ASSESSMENTS:					
Demographic; HIV status; PrEP Uptake; Relationship length; Drug Use Events; Problematic Drug Use; Condomless Anal Sex with casual partner; Relationship Functioning	X	X	X	X	X
	X	X	X	X	X

Sample Size

Results were generated by Monte Carlo simulation using Mplus. All estimates were based upon 10,000 sample replications and power was defined as the percentage of randomly generated samples in which the specified parameter was statistically significant. All models specified that individuals were nested within couples. Models focused on detecting between-condition differences at any one follow-up time-point. The main effects of the two interventions

were modeled at level 2. Given the pilot nature of this RCT, no a priori hypothesis was made about the size of the interaction effect anticipated. Therefore, all analyses were conducted under the conservative assumption that the interaction effect is of equivalent size and opposite direction. In this case, there is a significant effect of one treatment only at one level of the other.

Assuming 80% of the sample endorsed drug use at baseline, a sample of 70 couples has power approximately = .60 to detect a treatment effect associated with a 10% decrease in the odds of drug use at any follow-up time point. Similarly – assuming an average DAST-10 score of 2.0 at baseline – the study had power $\geq .60$ to detect a 0.5 SD difference in DAST-10 scores at any follow-up time point. CAS with casual partners and concurrent CAS with casual and main partners were both reported by approximately 26% of the sample at baseline. Under the most conservative default assumptions about the size and direction of the interaction term, this study has power approximately = 0.40 to detect a main effect associated with a 15% decrease in the odds of these variables. Under somewhat less conservative assumptions, assuming a null interaction effect, power to detect a treatment effect of this size was largely unchanged.

Recruitment

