The success of randomization, the presence of differential attrition, and between-group differences on safety indicators (relationship dissolution and IPV) were assessed using repeated-measures Analysis of Variance (ANOVA) for continuous variables. To account for the nesting of people-within-couples, between-condition differences in categorical variables were assessed by testing differences among Estimated Marginal Means in Generalized Estimating Equation (GEE) models. Where indicated, pairwise comparisons were conducted using a Least Significance Difference (LSD) post-hoc test.

Between-condition differences in primary outcomes were tested within a Latent Growth Curve (LGC) framework in Mplus (version 8.0). For each outcome, a latent intercept and linear slope were specified with the first post-intervention follow-up as the initial time-point. Binomial distributions were specified for Drug Use; CAS with casual partners; and concurrent CAS. DAST-10 scores were modeled using a Poisson distribution. Growth factors were specified at both the individual level (to allow for variability between partners within couple) and the couple level (reflecting dyadic assignment to condition). For each outcome, the direct effect of the CT video and SUM were included along with a CT-by-SUM interaction effect. In this procedure, a significant effect of treatment on the latent intercept factor indicates the presence of a group difference at that time point. Meanwhile, a significant effect on the latent linear slope factor indicates that the trajectory over time differs between groups. Missing data were handled within the context of full-information maximum likelihood estimation.

Data Monitoring

The study protocols are approved by the research ethics board of the principal investigator's academic institution and are registered with clinicaltrials.gov ([NCT03125915](https://clinicaltrials.gov/ct2/show/NCT03125915)).

Abbreviations

CAS	Condomless Anal Sex
CHTC	Couples HIV Testing and Counseling
CT	Assertive Communication Training
PRIDE	PRIDE Health Research Consortium
PrEP	Pre-Exposure Prophylaxis
SUM	Substance Use Module
YMSM	Young men who have sex with men (ages 18-29, unless otherwise specified)

DECLARATIONS

Availability of data and material: Not applicable as this manuscript contains no data.

Competing interests: The authors declare that they have no competing interests.

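### As described, the primary growth models make no use of each outcome's pre-randomization value; this gives up precision in the first-follow-up comparison, chiefly for DAST-10, by an amount that depends on an unstated correlation.

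*Combined protocol and SAP*

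**What the plan says.** The Data Analysis Plan specifies, for each outcome, that "a latent intercept and linear slope were specified with the first post-intervention follow-up as the initial time-point". It then names the predictors: "For each outcome, the direct effect of the CT video and SUM were included along with a CT-by-SUM interaction effect". No covariate is mentioned. On structure it adds "Growth factors were specified at both the individual level" and at the couple level, and on missing data "Missing data were handled within the context of full-information maximum likelihood estimation".

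The baseline values exist. Trial Design states "Baseline assessment is conducted prior to randomization and the receipt of intervention", and Blinding confirms that randomization followed the baseline assessment. The assessment table under Participant Timeline marks "Drug Use Events; Problematic Drug Use; Condomless Anal Sex with casual partner" at enrolment. Sample Size reports "CAS with casual partners and concurrent CAS with casual and main partners were both reported by approximately 26% of the sample at baseline", so baseline values were also observed for concurrent CAS, the fourth outcome modelled.

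The strata under Randomization are age discrepancy, relationship length and race/ethnicity. None is an outcome. No baseline-to-follow-up correlation appears anywhere.

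**The concern.** The trial has 70 couples in four conditions, and its own stated power is only about .40 to .60. In a trial of that size, chance differences between arms at baseline are not small. Neither the stratification nor the model as described removes their effect on the follow-up comparison. If baseline predicts follow-up, the treatment effect on the intercept carries more variance than it needs to, and data already in hand would reduce it. At stake is precision, and so power, for the comparison at the first follow-up.

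**Working it through.** **Inputs from the documents.** 70 couples (140 men) in a 2 x 2 design. DAST-10 planning effect 0.5 SD, power at least .60, baseline mean 2.0. Drug use 80% with a 10% reduction in odds; CAS 26% with a 15% reduction in odds.

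**Assumptions.** Equal allocation: 70 v 70 men for a main effect, 35 v 35 for one treatment at one level of the other. Two-sided alpha 0.05. Within-couple ICC 0 to 0.5. r = 0.3, 0.5, 0.7. Couples are randomized, so the r that matters is mainly that of couple means.

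**1. The plan's DAST-10 figure.** With noncentrality 0.5/sqrt(2(1+ICC)/n), 70 v 70 gives power .84 at ICC 0 and .68 at ICC 0.5, and reaches .60 at ICC of about 0.78. For 35 v 35 it is .55 at ICC 0. Alpha, ICC and the tested parameter are not stated, so the stated floor can be neither confirmed nor refuted. It serves below only as a starting point.

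**2. Chance baseline imbalance.** Its SD, in baseline SD units, is sqrt((2/n)(1+ICC)).

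| | ICC 0 | ICC 0.5 |
|---|---|---|
| 70 v 70 | 0.17 | 0.21 |
| 35 v 35 | 0.24 | 0.29 |

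This variation is already inside the unadjusted standard error. It is the source of the lost precision and is not counted again.

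**3. DAST-10 power with adjustment (linear approximation).** Residual variance falls by the factor 1 - r². Power = Phi(nc/sqrt(1 - r²) - 1.960).

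| Starting power | nc | r 0.3 | r 0.5 | r 0.7 |
|---|---|---|---|---|
| .60 (stated floor) | 2.213 | .64 | .72 | .87 |
| .84 (70 v 70, ICC 0) | 2.958 | .87 | .93 | .985 |

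The equivalent in extra couples is 70/(1 - r²) - 70 = 7, 23 and 67.

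**4. Cost of the covariate.** The variance inflation is 1 + 1/(70 - 4 - 1 - 1) = 1.0156, or about 1.6%. Break-even is r = sqrt(1 - 1/1.0156) = 0.12. Net of this cost, the first row becomes .63, .72 and .87.

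**5. Binary outcomes at the planned effects.** Sample Size gives power "to detect a treatment effect associated with a 10% decrease in the odds of drug use". From 80%, the odds go from 4.0 to 3.6, which is 78.3%. From 26%, they go from 0.351 to 0.299, which is 23.0%. An unpooled two-sided z-test with 70 v 70 gives power .057 and .070. The same 1 - r² formula moves these to .058/.060/.065 for drug use and .072/.076/.089 for CAS: under 1 and under 2 percentage points. That these values differ from the stated .60 and .40 is a separate matter.

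**6. DAST-10 growth model, simulated.** Assumptions: 70 couples, months 1, 3 and 6, Poisson mean 2.0, random intercepts and slopes at person and couple level, 20% monotone dropout, CT rate ratio 0.65 or 1, own baseline as log(1+baseline), 110 trials in each of three scenarios. The mean SE of the CT effect at month 1 fell from 0.151 to 0.144 (5%) at couple-mean r 0.30, and from 0.192 to 0.162 (16%) at r 0.56. The slope effect did not change (SD 0.048 either way). Adding the couple-mean baseline gave no further gain. Null rejection was 0.045 with and without adjustment (Monte Carlo SE about 2 points). All 990 fits converged, and 98-100% had a positive-definite Hessian.

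**The case against.** The plan is silent on covariates rather than excluding them, and its opening block refers readers to a publication for more detail. r is unknown; at 0.3 the gain is only 3 to 4 points. The simulation covers one outcome of four, shows nothing for the slope, and is small: with 110 trials an empirical SD carries about 7% Monte Carlo error, and 0.045 is weak evidence on type I error. Eligibility Criteria require a recent drug user in every couple, so the couple-mean drug-use baseline is mostly 0.5 or 1 and may predict little. The trial is a pilot, and its opening block points to results already reported, so adjustment cannot restore power to an analysis already done.

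Most of this stands as a limit on scope. It confines the point to the models as described, to the intercept, and chiefly to DAST-10. It does not remove the point, because a model run as written would leave baseline unused.

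Three stronger readings are tempting, and the documents do not support them. A reader might infer that the unadjusted comparison is biased; assignment is random, so it is not. A reader might treat chance imbalance as a second harm on top of lower power; the two are one cost. A reader might apply the 1 - r² gain to the stated .40 for CAS; that figure belongs to a binary outcome for which step 5 shows almost no gain at the planned effect.

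**Conclusion.** The point holds for the models as described: a pre-randomization measure of each outcome is collected and not used. The loss is precision of the treatment effect on the latent intercept. It is supported mainly for DAST-10, where power would rise from .60 to about .64, .72 or .87, or from .84 to about .87, .93 or .985, at r of 0.3, 0.5 or 0.7. These figures rest on an assumed r and a linear approximation, which is only indicative for a Poisson model; the simulated SE reductions of 5% and 16% point the same way. No slope gain was found, and no material power gain is shown for drug use or CAS. The change is worth making because it is cheap. Confidence is medium, since r is unknown.

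**What to change.** In the DAST-10 growth model, regress the latent intercept on the participant's own baseline DAST-10 score, entered as log(1+baseline), alongside CT, SUM and CT-by-SUM. Do not center it on the couple mean: a couple-centered value carries no between-couple information and cannot adjust a comparison of randomized couples.

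In the binary models, add the participant's baseline indicator in the same way where the model converges, and state in advance that the unadjusted model is used if it does not.

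Model the baseline covariate, so that participants with a missing baseline stay in under full-information maximum likelihood. Report the unadjusted model alongside, and state that adjusted odds ratios are conditional on baseline. For any outcome already analysed, keep the unadjusted model as primary and report the adjusted one as a labelled supplementary analysis.

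The cost is wording in the analysis plan and one coefficient per model beside the six treatment coefficients (three on the intercept, three on the slope). No new data are needed. The 1.6% variance cost is a net loss only if r is below about 0.12. Convergence must be checked in the full models: the binary models and their fitting in Mplus were not tested.

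### Does the plan need to name which contrast a significant CT or SUM coefficient represents when the model also contains their interaction?

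*Combined protocol and SAP*

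**What the plan says.** The Data Analysis Plan tests the primary outcomes in latent growth curve models. The intercept is placed at the first follow-up, and condition acts at couple level. For each outcome, "the direct effect of the CT video and SUM were included along with a CT-by-SUM interaction effect". It then explains how to read the two growth factors: for the intercept, "a significant effect of treatment on the latent intercept factor indicates the presence of a group difference at that time point"; the next sentence says that an effect on the slope means the trajectories differ. Neither the coding of CT and SUM nor the groups compared are stated.

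The Sample Size section calls the effects main effects. It says that no hypothesis was made in advance about the size of the interaction, and that "all analyses were conducted under the conservative assumption that the interaction effect is of equivalent size and opposite direction". It adds: "In this case, there is a significant effect of one treatment only at one level of the other". Power is given as about .60 for drug use, at least .60 for a 0.5 SD difference in DAST-10, and about 0.40 for condomless anal sex (CAS) with casual partners. The CAS figure is given "Under the most conservative default assumptions about the size and direction of the interaction term"; the section then says that, "assuming a null interaction effect, power to detect a treatment effect of this size was largely unchanged".

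The Project Summary describes the trial as "comparing the new CHTC+SUM to the standard CHTC protocol and testing the added efficacy of the CT component". The Objectives say: "It was hypothesized that these two experimental components would significantly decrease the occurrence and severity of drug use".

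**The concern.** With a product term in the model, a component's coefficient has no meaning until the coding is known. With 0/1 coding it is CT against no CT among couples without SUM. With centred coding it is the CT effect averaged over couples with and without SUM. In the planning scenario a component does nothing at one level of the other, so a significant coefficient reported simply as a group difference could be taken to apply to all couples when it applies to half of them. The interaction test might not warn the reader, because its power is low.

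A second doubt concerns the power statement. If the interaction assumption is conservative, removing it should raise power noticeably, yet the CAS power is said to have hardly moved. A reader could then wonder which effect .60 and .40 describe, and whether they are lower bounds.

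**Working it through.** **Inputs.** From the document: 70 couples, four conditions, 0.5 SD and a mean of 2.0 for DAST-10, and 26% with a 15% decrease in odds for CAS. Assumed because not stated: equal cells (70 x 2 / 4 = 35 men), two-sided 0.05, no dropout, and within-couple correlation (ICC) from 0 to 0.5, entering as a variance factor 1 + ICC.

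**1. The two contrasts.** Let the CT effect without SUM be b and the interaction c. The CT effect with SUM is b + c, and the averaged effect is b + c/2. With c = -b these are b, 0 and b/2. With c = 0 all three equal b. So the two candidate meanings differ by a factor of two in the planning scenario and coincide without interaction.

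**2. The plan's DAST-10 figure (at least .60).** On a Poisson scale with ICC 0, 0.5 SD is 0.5 x √2 = 0.707, so the mean falls from 2.0 to 1.293.
- Simple effect: ln(2/1.293) = 0.436; SE = √(1/(35 x 2) + 1/(35 x 1.293)) = 0.191; ratio 2.29; power 0.63.
- Averaged effect with c = -b: 0.218; SE = √[(1/(35 x 2) + 3/(35 x 1.293))/4] = 0.142; ratio 1.54; power 0.34.

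The simple effect reaches the stated figure only near ICC 0 (0.52 at ICC 0.3). An averaged effect that is itself 0.5 SD also reaches it (0.84 on the normal scale at ICC 0). The power figure therefore does not identify the coding.

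**3. The same comparison on the normal scale.** In SD units, SE(simple) = √(2(1+ICC)/35) and SE(averaged) = √((1+ICC)/35). The simple effect is 0.50.

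| ICC | Simple, either interaction | Averaged, c = -b | Averaged, c = 0 |
|---|---|---|---|
| 0 | 0.55 | 0.31 | 0.84 |
| 0.3 | 0.45 | 0.25 | 0.74 |
| 0.5 | 0.40 | 0.23 | 0.68 |

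**4. Taking the stated power as given.** Power .40 is a noncentrality of 1.71, and .60 is 2.21.
- If these belong to the simple effect, the averaged effect under c = -b has 1.71/√2 = 1.21 (power 0.23) and 2.21/√2 = 1.57 (power 0.35). The interaction test has the same values.
- Given a significant simple effect, the interaction would be non-significant in 54% of trials (at .40) or 48% (at .60). If the coefficient is the averaged effect, the shares are 60% and 40%.
- If .40 belongs to an averaged effect with the simple effect held fixed, removing the interaction gives 2 x 1.71 = 3.41, power 0.93. That is not unchanged.

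**5. Whether step 4 can be relied on for CAS.** It accepts .40, which the stated effect does not produce. With an odds ratio of 0.85, 26% becomes 23.0%; ln 0.85 = -0.163; SE at ICC 0 = 0.557; ratio 0.29; power about 0.06. The averaged effect with the simple effect held fixed has power about 0.05 with c = -b and 0.07 with c = 0, which is also largely unchanged. To reach .40, the simple effect would need an odds ratio of about 0.31 (ICC 0) to 0.21 (ICC 0.4). Moreover, if the averaged effect is held fixed and 26% is the CHTC-alone cell, one calibration gives 0.59 without interaction against 0.40 with it. There the assumption is conservative.

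**6. What naming the contrast would alter in the analysis.** Four conditions are described by four parameters on each growth factor. Changing from 0/1 to centred coding re-expresses the same four cell values: same fit, same likelihood, same handling of missing data. Simple effects, averaged effects and the interaction are linear combinations of one set of estimates and their covariance matrix.

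**The case for a change.** The strongest case for a change is that the quoted sentence, with its slope counterpart, is the only reading rule for the primary outcomes. The pairwise LSD comparisons belong to the randomization, attrition and safety checks. The rest of the document does not settle the matter: main effects suggests averaging, the comparison of CHTC+SUM with standard CHTC suggests a simple effect, and a product term that cancels the effect at one level fits 0/1 coding but also ±1 coding. The Objectives speak of significant effects, a non-significant interaction gives little reassurance, and a few words would close the gap. Unstated coding also leaves some freedom in which coefficient to headline.

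What stands is that the contrast is unnamed, that the two meanings differ by a factor of two under the planning assumption, and that .60 and .40 cannot be assigned to one of them with certainty.

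The rest is weaker. The sentence contrasts intercept with slope and does not say the interaction will be disregarded; a simple effect is a group difference, so the sentence is incomplete rather than wrong. The equal-and-opposite interaction is a planning default adopted because nothing was predicted, so the shares of 40% to 60% describe a hypothetical. They arise from low interaction power with 70 couples, which a label would not cure. The argument against the word conservative rests on a stated power that the literal effect size does not support. It also uses a remark made only about the CAS outcomes, and it fails in at least one calibration.

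**Conclusion.** No change to the plan follows. This is missing detail that an analyst fills sensibly: whoever fits the model must choose a coding, and reporting a coefficient beside its interaction requires saying what it compares. Both contrasts are legitimate, and neither needs another model or more data. Deleting or qualifying the word conservative would change no estimate, test or sample size.

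The difference between the readings is a factor of two on the model scale if the interaction is equal and opposite, and nil if there is none. In power terms for a 0.5 SD simple effect under the equal-and-opposite interaction, it is 0.55 against 0.31 at ICC 0 and 0.40 against 0.23 at ICC 0.5. These figures rest on equal cells, two-sided 0.05 and no dropout. The conclusion also rests on the interaction being fitted for every primary outcome, as the plan says, and on the study being a pilot of feasibility, acceptability and preliminary efficacy. A reader of the results should check which contrast is reported before generalizing a component's effect to couples who also received the other component.
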